### **Exploratory Aims**

To compare other parameters of ECT when used with ketamine anesthesia to that with methohexitol anesthesia. These parameters are:

1. Seizure duration.
2. Seizure morphology.
3. Hemodynamic changes during ECT procedure.
4. Postictal behavioral complications such as agitation or psychosis.
5. To detect differences in brain activation.

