pain compared to control patients, and pain is closely related to the pathophysiology of depression, ketamine functioned not only as an analgesic but also as an antidepressant.

Ketamine had previously been observed to improve mood after adjunctive as well as inductive doses. Yilmaz recognized that anesthetic doses of ketamine led to a long-term remittance of behavioral despair, an animal model of depression, in rats. The rats were subject to two forced swim tests, the second of which followed a single injection of saline or of anesthetic ketamine. The ketamine-injected animals immediately showed significantly less signs of behavioral despair (less immobility and more escape behaviors) for up to ten days compared to their control counterparts. This study suggests that ketamine may have a similar antidepressant effect in humans.

Furthermore, the significant mood-elevating effect of ketamine observed in Yilmaz's rats indicates that NMDA receptors and the glutaminergic system are involved in the pathophysiology of behavioral despair and depression. The prolonged effect of ketamine, particularly significant considering ketamine's short half-life of only two hours, may be due to a long-term change in glutamate activation. The brain areas most likely implicated in this long-term change are the frontal cortex, hippocampus and amygdala. These sites house learning and memory, and therefore, the learned helplessness displayed in the forced swim tests. It is also a possibility that ketamine's interaction at the NMDA receptor could affect mood and behavior through secondary effects on the monoaminergic and opiate systems. Similarly, ketamine has a weak affinity for the mu opiate receptor and a weak antagonism for a dopamine transporter.

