Since this is a pilot study, the goal is to estimate the magnitude of the effect sizes for use in designing a subsequent study. With 12 patients randomized to each of the two treatment groups, there is only 45% power with an alpha level of 5% to detect a difference of 50% remission rate in the methohexital group and an 80% remission rate in the ketamine group at visit 8. For the other aims, which look at the change in scores on various rating scales over time, there will be 80% power with an alpha level of 5% (2-sided) to detect a difference between the slopes (measuring rate of change in scores on tests per visit) for the two treatment groups of magnitude  $0.05\sigma$ , where  $\sigma$  is the standard deviation of scores in either treatment group at a single visit. If, for example, the standard deviation of the HRSD scores is 5.0, then there will be power to detect an increased rate of improvement in the ketamine group of 0.25 points per visit, corresponding to an average improvement of 2.0 more points per 8 visits in the ketamine group than whatever improvement is observed in the methohexital group (Diggle et al 1995).

Given the recognition that, with the small sample size, power will be low, the primary focus of analysis is to determine whether ECT with ketamine anesthesia compared to ECT with methohexital anesthesia produces a clinically significant effect, i.e., one that, even if it does not reach statistical significance, would justify a larger clinical trial to replicate effect size. We expect a mean number of 8 treatments to remission based on the results of a Consortium for Research in ECT paper.

Our specific hypothesis is that ECT will decrease functional connectivity in the Default Mode Network (time-wise hypothesis). We also think that the decrease in the expression of this network will correlate with the effectiveness of the ECT, or at least will show a difference

between responders and non-responders (group-wise hypothesis). In order to detect network changes, we will calculate seed based correlation, ICA network expressions and amplitude measures of the networks.

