### ICA-Dual regression

The dual-regression approach will be used to identify, within each subject's fMRI data set, subject-specific temporal dynamics and associated spatial maps. This involves (i) using the full set of group-ICA spatial maps in a linear model  $t$  (spatial regression) against the separate fMRI data sets, resulting in matrices describing temporal dynamics for each component and subject, and (ii) using these time-course matrices in a linear model  $t$  (temporal regression) against the associated fMRI data set to estimate subject-specific spatial maps. Finally, the different component maps are collected across subjects into single 4D images (1 per original ICA map, with the fourth dimension being subject identification) and tested voxel-wise for statistically significant differences between groups using nonparametric permutation testing (5,000 permutations). This results in spatial maps characterizing the between-subject/group differences (Figure 3).

[figure not shown]

Figure 3. Dual regression

The biggest advantage of this technique is that it will create functionally and anatomically corresponding spatial maps for every individual, thus making the patterns comparable across subjects. In traditional approaches individual ICA resulted in components where no straightforward comparison was possible.

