### **Group analysis**

Our main goal in our analysis is to determine group-wise effects. The inter-subject variability however poses the main obstacle to gain meaningful effects. We will use our time-wise data to “subtract” measures between time points in the same individual, and analyze our data with repeated measure ANOVA (one factor is time point (intra-subject), other is group (inter-subject)).

Group comparison of the seed based correlation measures is straightforward, correlation values between the vmPFC and other DMN regions and subgenual cingulate will be used to detect any interaction between factors (time and group (responders and non-responders)).

The group analysis of ICA networks will be carried out by dual regression method, as it is presented on Figure 3. Individual network patterns will be obtained, and these individual patterns will be used in a second level analysis with SPM, where voxel based repeated measure ANOVA will be calculated. Similarly individual amplitude maps will be analyzed with SPM.

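### The imaging plan specifies no analysis by randomised anesthetic, so one exploratory aim has no matching analysis and the responder contrast is open to modest confounding

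*Combined protocol and SAP*

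**What the plan says.** **The aim.** The Exploratory Aims open with "To compare other parameters of ECT when used with ketamine anesthesia to that with methohexitol anesthesia". The fifth item in that list is "To detect differences in brain activation". Patients are randomised 1:1 between the two agents (1. Study Overview).

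**The imaging analysis.**
- *13. Data Analysis*: the between-group imaging hypothesis is a difference "between responders and non-responders (group-wise hypothesis").
- The paragraph for Aim 2 B in the same section gives a general linear model for task fMRI and names no between-arm contrast.
- *ICA-Dual regression*: component maps are "tested voxel-wise for statistically significant differences between groups using nonparametric permutation testing (5,000 permutations"). The groups are not named.
- *Group analysis*, general statement: a repeated-measures ANOVA in which "one factor is time point (intra-subject), other is group (inter-subject"). Group is again not named.
- *Group analysis*, seed-based measures: the test is for any "interaction between factors (time and group (responders and non-responders")).
- *Sample Size and Power*: differences between time points only.

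The only definition of *group* in these sections is response status. *Responder* itself is not defined; d. Outcome Criteria defines remitters and non-remitters.

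**Who is scanned.** Patients found ineligible for the ketamine part may enter for imaging only (text after the eligibility criteria in section 3), and healthy volunteers are scanned as controls (1. Study Overview).

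**The concern.** There are two consequences.

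First, a stated aim has no analysis. With *group* undefined in two places, whether the anesthetic comparison is made, and how, can be settled after the data are seen.

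Second, response is observed after randomisation and may depend on arm. If ketamine raises the response rate and also alters connectivity by a route other than response, part of the ketamine effect will appear in the responder-by-time interaction. The same holds for Secondary Aim B(c) and (d), which relate networks to clinical outcome and to side effects, because the Hypothesis section expects ketamine to improve both. A network reported as a correlate of response to ECT could then partly reflect the drug. The healthy controls cannot reveal this, since nothing in the plan gives them an anesthetic.

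**Working it through.** The plan gives no figure for this contrast, so there is none to reproduce. The check has two parts.

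**Part 1: is arm specified anywhere?** Every imaging analysis listed above uses time point, response status or an undefined group. None names the anesthetic.

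**Part 2: how large could the confounding be?**

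Inputs from section 13: 12 patients per arm, and a power scenario of "a difference of 50% remission rate in the methohexital group and an 80% remission rate in the ketamine group at visit 8". Two assumptions are needed: remission stands in for the undefined *response*, and ketamine has a direct effect of d SD on the imaging change. The documents give no value for d.

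*Step 1, expected counts.*
- Remitters: 12 × 0.8 = 9.6 ketamine and 12 × 0.5 = 6.0 methohexital, total 15.6.
- Non-remitters: 12 × 0.2 = 2.4 ketamine and 12 × 0.5 = 6.0 methohexital, total 8.4.

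*Step 2, ketamine exposure by outcome.*
- Remitters: 9.6/15.6 = 61.5%.
- Non-remitters: 2.4/8.4 = 28.6%.
- Gap: 32.9 percentage points.

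*Step 3, strength of the arm–remission association.* Overall remission is 15.6/24 = 0.65. With equal arms, phi = (0.8 − 0.5) × 0.5 / √(0.65 × 0.35) = 0.15/0.477 = 0.31, so phi² is about 0.10.

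*Step 4, spurious responder difference* = 0.329 × d.

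*Step 5, false-positive rate.* Simulation with 12 v 12, about 8,000 runs per setting, change scores, a two-sided 5% test and no true responder effect:

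| Assumed d (SD) | Spurious difference (SD) | False positives, no arm term | False positives, arm in model |
|---|---|---|---|
| 0 | 0 | 5.4% | 5.3% |
| 0.5 | 0.16 | 6.3% | 5.3% |
| 0.8 | 0.26 | 8.4% | 4.8% |
| 1.0 | 0.33 | 10.5% | 4.9% |

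With 65% remission in both arms, the rate without an arm term stays at about 5% for every d.

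*Step 6, what an arm contrast could detect.* For one prespecified change score, 12 v 12, two-sided 5% t-test, power is 22%, 47% and 65% for effects of 0.5, 0.8 and 1.0 SD. The effect detectable with 80% power is about 1.20 SD, or about 1.32 SD with 10 v 10. Voxel-wise correction would lower power further.

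**The case against.** **The arm contrast may still be intended.** *Group* is undefined in the general ANOVA statement and in the dual-regression test, and Figure 3, to which the ICA group analysis refers, is not available here. This stands. A reader might infer that the anesthetic comparison will never be made; the documents show only that the readable text does not specify it.

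**The 80% and 50% are a power scenario, not a forecast for the groups compared.** They refer to visit 8. A non-remitter, premature exits aside, needs at least 10 treatments (d. Outcome Criteria), and a course may run to 15 (6. ECT Procedures). The trial hypothesises fewer treatments to remission, which concerns speed. If ketamine only speeds remission, final rates converge and the bias shrinks toward zero. This stands, and it makes the figures an illustration.

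**Response status is a weak marker of arm.** A reader might infer that it is a proxy for the anesthetic, or that the responder contrast cannot separate the two. Phi of 0.31 and 6.0/15.6 = 38% of remitters on methohexital do not support either reading.

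**A direct ketamine effect on imaging is not established.** The Antidepressant Effect section says "The brain areas most likely implicated in this long-term change are the frontal cortex, hippocampus and amygdala", but this is speculation from a rat experiment. A reader might infer that the protocol expects lasting ketamine changes in its patients; it does not say so. What remains is plausibility: the passage raises the possibility, and exploratory aim 5 sets out to look for a difference.

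**Scope.** The lead imaging hypothesis, a fall in default-mode connectivity after ECT, is within-subject and is not touched by the missing arm adjustment in the responder contrast. Aim B(c) and (d) speak of correlation, not mechanism. Aim 5 is the last exploratory item in a 24-patient pilot, and items 1 to 4 have no explicit analysis in section 13 either. All of this limits the weight of the point. It does not justify leaving arm out: the pilot's declared purpose is to estimate effect sizes, which an arm-by-time estimate would serve.

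**Conclusion.** The point holds in limited form. A stated comparison between randomised arms has no specified imaging analysis; this follows from the text alone and does not depend on d. The unadjusted responder contrast, and the outcome and side-effect correlations, are open to modest confounding. That requires ketamine both to change response (or side effects), which is the trial's hypothesis, and to change the imaging measure directly, which is plausible but not shown.

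Under the visit-8 scenario, with remission standing in for response, the spurious responder difference is about 0.33d SD. The false-positive rate is about 6% to 11% for assumed d of 0.5 to 1.0, against a nominal 5%. It is unaffected if d is zero or final remission rates are equal. The plan should be changed, but the documents do not support saying that the responder findings would be uninterpretable.

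**What to change.** In the Group analysis section, with matching wording in ICA-Dual regression and in the task-fMRI paragraph:

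1. Define *group* for each imaging analysis, and define *responder*.
2. Add an arm-by-time contrast, in randomised patients only and labelled exploratory, as the analysis of exploratory aim 5. Report it as an estimate with its confidence interval.
3. Report the patient responder-by-time and side-effect analyses with arm and arm-by-time included, next to the unadjusted results.
4. Keep imaging-only patients out of the arm contrast, because they are not randomised and including them would lose its protection. Record the anesthetic they received and use it only as a covariate in the responder analysis.
5. Do not apply the arm factor to models that include healthy controls.

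**Cost.** No new procedure is needed for randomised patients, whose arm is already known; imaging-only patients need one recorded item. The models lose one between-subject degree of freedom plus the arm-by-time terms (two, with three scans). Adjustment rests on a sparse cell, about 2.4 ketamine non-remitters in the scenario above. The arm contrast has 80% power only for about 1.2 SD at 12 v 12, before voxel-wise correction, so a non-significant result should not be read as evidence of no difference.

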have examined regional changes in blood flow or glucose consumption before and after ECT. However, the results of these studies were sometimes contradictory and this type of methodology was not suited to detect possible changes in brain networks. In this last decade novel fMRI techniques have became available to measure and evaluate networks in the brain. Hence, in this pilot study, we will also collect longitudinal MRI data (once before ECT and twice after ECT) to gain novel insight into the effect of ECT at a deeper level.

In addition, we will also explore other parameters of ECT, such as seizure duration and morphology as well as hemodynamic and behavioral changes when using ketamine versus methohexitol for ECT.

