### **Secondary Aim B**

To use resting state and task related fMRI to identify ECT related functional network changes in the brain. Using resting state fMRI before and after ECT, we will (a) identify networks modulated by ECT (defined as a decrease or increase in functional connectivity from baseline to follow up scans), and we will (b) follow up their expression in the upcoming weeks, we will (c) identify functional networks of the brain which are correlated with superior clinical ECT outcome and we will (d) identify functional networks of the brain which are correlated with side effect profiles.

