can only be measured a couple of weeks later as the activation increases. Also, note that increases were mainly demonstrated with rCBF measurements, while decreases were measured with glucose metabolism. At first glance this seems to be somewhat counterintuitive, but discrepancies in metabolism and blood flow actually might reflect something very profound about the biochemical reactions in a brain area. The ideal combination would be to measure the oxygen consumption and the glucose metabolism, as it was recently shown that this might have important implications.

ECT is a form of psychosurgery?

As previously mentioned, functional neuroimaging studies in depression consistently show alterations in the subgenual ACC. The subgenual ACC is now being targeted with deep brain stimulation (DBS) and this has shown to be an effective treatment. Originally it was thought that the basis of this type of treatment is that it causes a reversible lesion at a specific region. However, it has also been shown that there are other areas in the brain that can be effectively inhibited for the treatment of depression. Interestingly, these areas are all connected to the fronto-striatal network, and at this point it is thought that the stimulation not only affects one node in the brain, but through that node it influences the work of a complete neuronal network (fronto-striatal network). Can it be that the effect of ECT is also mainly dependent on its ability to alter neuronal networks in the brain?

The main theoretical question behind this study is whether ECT exerts its effect primarily by altering networks? Can we think about ECT as a crude way of doing DBS? With the help of advanced network paradigms and with the use of resting state fMRI techniques, can we potentially develop ECT that will be the outpatient equivalent of a DBS procedure?

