### **Sample Size and Power**

The primary objective of this study is to examine and validate the differences in neuroimaging changes and network expressions across different time points during the ECT treatment. We will use repeated measure ANOVA to analyze each of the neuroimaging measures between different timepoints. Traditional power analysis in neuroimaging is challenging not only because of the inherent multiple comparisons in our studies, but also due to the fact that different voxels have different signal to noise ratio, thus effect sizes. One possible approach would be to estimate the

effect size. In order to do that, we have to estimate the distribution of the magnitude of signal change and the within subject and between subject variance. In a motor area the signal change can be well above 1%, but with cognitive or perception tests the signal is usually around 0.5-1%. According power analysis calculations with these parameter estimates it was shown that 80% power can be reached with  $N=20$  sample size.Indeed, targeting for 20 subjects in neuroimaging studies is a common practice.

**Future Studies:** MRI images and diagnostic information will be kept in an IRB-approved data repository (IRB # 06.04.089; P.I.: [name]). All study information will be kept private and identifiable information will only be released with participant permission. Participants in the current study may also be contacted about the possibility of participating in future studies.

Funding source: Brain and Behavior Research Foundation: NARSAD Young Investigator Grant

Funding source: NIMH Advanced Center for Interventions and Services Research.

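### Secondary Aim B picks networks by the change they showed and then describes that change in the same patients, so the effect sizes of discovered networks are inflated and, under one reading, a partial return at scan 3 is built in

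*Combined protocol and SAP*

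**What the plan says.** Secondary Aim B has four parts. Part (a) is to "identify networks modulated by ECT (defined as a decrease or increase in functional connectivity from baseline to follow up scans". Part (b) is to "follow up their expression in the upcoming weeks". Parts (c) and (d) look for networks by their correlation with clinical outcome and with side effects. The imaging data are "longitudinal MRI data (once before ECT and twice after ECT", that is, three scans per patient.

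The Group analysis section gives the search for the ICA networks: "these individual patterns will be used in a second level analysis with SPM, where voxel based repeated measure ANOVA will be calculated". That sentence describes a test over whole maps and contains no selection step; the selection is in the wording of the aim. Amplitude maps have a cluster-level correction, and dual-regression group differences are tested by permutation. Neither the Data Analysis section nor the imaging sections after it mention a held-out sample, cross-validation or any other independent estimate for a discovered network.

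The imaging sample-size text says: "The primary objective of this study is to examine and validate the differences in neuroimaging changes and network expressions across different time points". For the pilot, Data Analysis says "the goal is to estimate the magnitude of the effect sizes for use in designing a subsequent study".

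The plan also has measures that do not depend on the observed change. There are six seeds at published coordinates, three of them in the default mode network, and a named-region comparison of responders with non-responders over time.

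**The concern.** A network that qualifies because it changed has, on average, measurement error pointing the same way as the change. Estimating the change in the same scans counts that error as effect. Correcting for multiple testing limits how many false networks qualify, but does not remove the bias in those that do.

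A second effect arises if the qualifying contrast is scan 2 against scan 1. The scan 2 error is then extreme on average and scan 3 is not, so scan 3 moves part of the way back even when nothing happened. Part (b) asks about exactly this later course. At stake are the reading of that course, the use of the word validate for it, and any effect size carried into the next study.

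**Working it through.** **Inputs.** Three scans per patient (Rationale). N = 24 randomised (Study Overview) and N = 20 (imaging Sample Size and Power). Z>2.3 is the plan's cluster-forming cut for ALFF/fALFF only; using it as a stand-alone, uncorrected selection rule is an assumption. Equal error variance and a within-patient correlation of 0.5 are also assumptions. Changes are in SD units of the measure, so the error SD is √0.5 = 0.707.

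**1. The plan's own figure.** The plan states: "According power analysis calculations with these parameter estimates it was shown that 80% power can be reached with" N = 20. This cannot be reproduced, because the variances, alpha and sidedness are not given. For scale, a paired t-test with N = 20 and 80% power detects a standardised change of 0.66 (two-sided 5%) or 0.58 (one-sided 5%).

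**2. Why a return appears.** Let e1, e2, e3 be the scan errors with variance σ², and let ρ be the correlation of e2 with e3 (e1 independent).

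- Var(e2 − e1) = 2σ² and Cov(e2 − e1, e3 − e2) = −(1 − ρ)σ².
- The expected return, as a share of the selected change, is (1 − ρ)/2: 50% for ρ = 0, 35% for ρ = 0.3 and 25% for ρ = 0.5.
- If the change is defined as (e2 + e3)/2 − e1, its covariance with e3 − e2 is zero, so there is no false return.
- The signs are symmetric: a selected increase is followed by a partial fall.

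**3. Size of the inflation.** With N = 24 the SD of the scan 1–2 change is √(2 × 0.5) = 1, so its SE is 1/√24 = 0.204. With known variance, the mean beyond Z = 2.3 is 0.204 × φ(2.3)/(1 − Φ(2.3)) = 0.204 × 2.64 = 0.54. Simulation with estimated variance gives:

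| Setting (selected decreases) | Scan 1 to 2 | Scan 2 to 3 |
|---|---|---|
| N = 24, no true change, selected on scan 1 v 2 | −0.51 | +0.25 |
| N = 20, the same | −0.55 | +0.28 |
| N = 24, no true change, selected on both follow-ups | −0.44 | 0.00 |
| N = 24, true lasting decrease of 0.30 | −0.58 | +0.14 |

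In the first row the return is nominally significant in about 21% of selected null networks, and a lasting decrease (scan 3 v 1) also in about 21%, against 2.5% each in that direction without selection. These rates are conditional on a null network having been selected (about 1.1% are, per direction). They are not trial-level error rates.

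At N = 20 the average standardised change in selected null networks is 0.66, the same as the two-sided detectable change in step 1.

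**4. Correlations, parts (c) and (d).** On the Fisher scale with 24 patients, SE = 1/√21 = 0.218. The cut is 2.3 × 0.218 = 0.502, that is r = 0.46. A true r of 0.30, once selected, is reported as about 0.55.

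**5. Consequence for sizing.** For a mean change, the required n scales with 1/d². Using 0.58 when the truth is 0.30 makes the next study too small by a factor of (0.58/0.30)² = 3.7.

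**6. Do the existing features help?**

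- Ten healthy controls: patients against controls in selected null decreases still reject in 34%.
- Measures fixed in advance: mean changes 0.00 and 0.00, with 5.0% rejection for scan 1–2.
- Responder-by-time test, even after selection on time: 5.3% (10/10 split) and 4.5% (13/7), near nominal.

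**7. Does leave-one-patient-out repair it?** Not if applied only to networks already found in all patients. With one measure per network it changes nothing (−0.51 and about +0.24). In smoothed searches of 20, 100 and 500 voxels the null drop was still −0.46, −0.40 and −0.26. The residue varies strongly with the set-up, so only its direction should be relied on. Run in every fold without that condition, the null estimate is close to zero.

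**The case against.** Several points against the concern stand.

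- The Group analysis sentence is a whole-map test. The select-then-follow rule comes from the aim's wording, and no two-step extraction is written out.
- A reader might infer that the protocol expects a decrease followed by recovery, and that noise manufactures its hypothesis. The documents do not support this. The stated hypothesis is a decrease in default mode connectivity, with no recovery. The remark that the therapeutic effect "can only be measured a couple of weeks later as the activation increases" belongs to a review of PET and blood-flow activation studies. Selection in part (a) is also two-sided.
- A reader might infer that the whole imaging analysis is circular. It is not: the fixed seeds and the named-region comparison are not chosen by their change.
- Part (a) does not say which follow-up scan defines the change. If both do, the false return disappears.
- The Z>2.3 rule is borrowed, and the r = 0.46 cut follows from it; neither is a selection rule in the plan. Stricter thresholds select fewer networks.
- The effect-size sentence in Data Analysis sits beside the clinical power statements. No text says that voxelwise imaging effects will size a study.

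These points limit the scope and make the exact sizes uncertain. They do not remove the inflation in discovered networks, which occurs under either reading of the follow-up scans, and nothing in the plan bars those estimates from later use.

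**Conclusion.** The concern holds for networks discovered under Secondary Aim B and reported from the same scans. Their effect sizes are biased away from zero: 0.44 to 0.51 SD from pure noise with 24 patients, depending on which scans define the change, and 0.58 instead of 0.30 SD for a true lasting decrease selected on scan 1 v 2. A false partial return of 25 to 50% of the selected change, in either direction, is added only if scan 1 against scan 2 is the selecting contrast. The sizes rest on the assumed correlations and the assumed uncorrected cut; the direction of the bias does not. The default mode hypothesis tested on fixed seeds is unaffected. This is a secondary aim of a pilot, but the bias is systematic and cheap to contain, so the plan should be changed.

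**What to change.** In Secondary Aim B and the Group analysis section:

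1. Test part (b), the course over scans 1, 2 and 3, on the default mode measures fixed in advance (the three default mode seeds and the default mode component), whether or not they emerge in part (a).
2. Label the courses and effect sizes of networks found by whole-brain search in parts (a) to (d) as descriptive and selection-biased, and state that they will not be used to size the next study.
3. If a less biased estimate is wanted for discovered networks, repeat the whole selection inside each leave-one-patient-out fold, measure the left-out patient, and report the result whether or not the full-sample search finds a network.

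Items 1 and 2 cost wording and a little analysis. Item 3 costs about 24 reruns of the group step, each with one patient fewer. The reported effects will look less favourable. No new data are needed.
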